#### Parameters with no CTCAE grade defined

Laboratory abnormalities will be tabulated (count and percentage) for each non-gradable parameter by the worst on-treatment abnormality. Shifts from baseline to worst abnormality (separately for high and low criteria) during the on-treatment period will also be tabulated. The denominator to calculate percentages for each laboratory parameter is the number of patients in the cohort dose level. Subjects without baseline or post-baseline results for a given parameter will be presented in the "Missing" category and will contribute to the denominator.

#### Liver Function Elevation and Possible Hy's Law Cases during On-Treatment Period

ALT, AST and Total Bilirubin are used to assess possible drug induced liver toxicity. The ratios of test result over upper limit of normal (ULN) will be calculated and classified for these three parameters during the on-treatment period.

A summary of liver function tests will include the following categories. The number and percentage of subjects with each of the following during the on-treatment period will be summarized overall and by dose level:

- ALT ≥ 3×ULN, ALT ≥ 5×ULN, ALT ≥ 10×ULN, ALT ≥ 20×ULN
- AST ≥ 3×ULN, AST ≥ 5xULN, AST ≥ 10×ULN, AST ≥ 20×ULN
- (ALT or AST) ≥ 3×ULN, (ALT or AST) ≥ 5×ULN, (ALT or AST) ≥ 10×ULN, (ALT or AST) ≥ 20×ULN
- Total Bilirubin ≥ 2×ULN
- Concurrent ALT ≥ 3×ULN and TBILI ≥ 2×ULN
- Concurrent AST ≥ 3×ULN and TBILI ≥ 2×ULN
- Concurrent (ALT or AST) ≥ 3×ULN and TBILI ≥ 2×ULN
- Concurrent (ALT or AST) ≥ 3×ULN and TBILI ≥ 2×ULN and ALP > 2×ULN
- Concurrent (ALT or AST) ≥ 3×ULN and TBILI ≥ 2×ULN and ALP ≤ 2×ULN or missing

Concurrent measurements are those occurring on the same date.

Categories will be cumulative, i.e., a subject with an elevation of AST  $\geq$ 10×ULN will also appear in the categories  $\geq$ 5×ULN and  $\geq$ 3×ULN.

An evaluation of Drug-Induced Serious Hepatotoxicity (eDISH) plot will also be created by graphically displaying peak serum ALT (/ULN) vs peak Total Bilirubin (/ULN) including

reference lines at ALT  $\geq 3$ xULN and bilirubin  $\geq 2$ xULN. The display will be divided into 4 quadrants by the lines through ALT  $\geq 3$ ×ULN and Total Bilirubin  $\geq 2$ ×ULN. The left lower quadrant is then considered normal or insignificant elevations in liver chemistries, the left upper quadrant indicates patients with possible Gilbert's cholestasis; the right upper quadrant are the possible Hy's Law patients; the right lower quadrant is possible Temple's Corollary (patients with ALT  $\geq 3$  x ULN but not satisfying Hy's Law). Different symbol will be used for different cohort dose levels.

# 15.3.2 Other laboratory parameters

All other parameters collected on the eCRF will be listed in dedicated listings presenting all corresponding collected data-fields on the eCRF.

Urinalysis: all urinalysis parameters

Hormones: free thyroxine (T4) and thyroid-stimulating hormone (TSH)

Serology: HIV and hepatitis

Pregnancy test

# 15.4 Vital Signs

Analysis set: SAF

The maximum changes of vital sign measurements from baseline to maximum change during the on-treatment period will be grouped as follows:

Table 9: Vital Signs Summary Categories

Vital Sign Baseline Category	Change from Baseline Category
Body temperature increase	<1°C, 1-<2°C, 2-<3°C, ≥3 °C
Heart rate increase from baseline <100 bpm; ≥ 100 bpm	≤20 bpm, >20 – 40 bpm, >40 bpm
Heart rate decrease from baseline <100 bpm; ≥ 100 bpm	≤20 bpm, >20 – 40 bpm, >40 bpm
SBP increase from baseline <140 mmHg; ≥ 140 mmHg	≤20 mmHg, >20 – 40 mmHg, >40 mmHg
SBP decrease from baseline <140 mmHg; ≥ 140 mmHg	≤20 mmHg, >20 – 40 mmHg, >40 mmHg
DBP increase from baseline <90 mmHg; ≥ 90 mmHg	≤20 mmHg, >20 – 40 mmHg, >40 mmHg
DBP decrease from baseline <90 mmHg; ≥ 90 mmHg	≤20 mmHg, >20 – 40 mmHg, >40 mmHg
Respiration rate increase from baseline <20 bpm; ≥ 20 bpm	≤5 bpm, >5 – 10 bpm, >10 bpm
Respiration rate decrease from baseline <20 bpm; ≥ 20 bpm	≤5 bpm, >5 – 10 bpm, >10 bpm

The following summaries will be prepared for vital sign parameters as grouped above considering only participants with post-baseline values:

- Maximal shifts (changes in categories)
- Listing of highest change per participant

An additional participant data listing will present all pertinent vital signs details collected throughout the course of the study.

#### 15.5 Other Safety or Tolerability Evaluations

Analysis set: SAF

#### 15.5.1 12-Lead Electrocardiogram

The incidence and percentage of subjects with potentially clinically significant abnormalities (PCSA) for 12-lead ECG parameters will be summarized during the on-treatment period. The PCSA criteria are provided in the Table 10.

Table 10: Potentially Clinically Significant Abnormalities Criteria for ECG

Test	Potentially Clinically Significant Abnormalities (PCSA) Criteria
Heart Rate	≤ 50 bpm and decrease from baseline ≥ 20 bpm≥ 120 bpm and increased from baseline ≥ 20 bpm
QRS	≥ 120 ms
QTcF absolute (a)	>450 ms - <=480 ms >480 ms - <= 500 ms >500 ms
QTcF change from baseline (a)	Increase: >30 ms - <= 60 ms >60 ms
QTcF change from baseline	Decrease: >30 ms - <= 60 ms >60 ms

a) QTcF (Fridericia's Correction) =  $QT/\sqrt[3]{RR}$  (RR-interval is measured in seconds) will be summarized as collected in eCRF.

Listings of ECG parameters will be provided including the data collected in eCRF and the change from baseline. A separate listing for PCSA will be created.

# 15.5.2 Eastern Cooperative Oncology Group Performance Status

Eastern Cooperative Oncology Group Performance Status (ECOG PS) will be summarized using a shift table showing baseline versus worst post-treatment value. The information will come from the "ECOG Performance Status" eCRF page.

Listings of each participant's ECOG PS over time will be provided.

### 16 Analyses of Other Endpoints

#### 16.1 Pharmacokinetics

Population: PK analysis set

Non-compartmental computation of M3814 and 0-demethylated product M467 (if available) PK parameters will be performed using the computer program Phoenix® WinNonlin® Version 8.0, or higher (Pharsight Corporation, a Certara Company, Princeton, New Jersey). The statistical software SAS® (Statistical Analysis System, SAS-Institute, Cary North Carolina), Version 9.2, or higher, will be used to produce tables, listings, and figures. Figures will be prepared with SAS Version 9.2, or higher.

Avelumab tables, listings, figures, and parameters will be computed using SAS.

Pharmacokinetic parameters will be calculated using standard non-compartmental methods, the actual administered dose, and actual elapsed time from dosing.

Pharmacokinetic concentrations of M3814 would be pooled with data from other studies to conduct a population PK analysis. A non-linear mixed effect approach would be used to characterize the blood concentration time profile of M3814 following multiple doses and to evaluate the PK inter-individual variability and the covariates that are predicting this variability. Provided sufficient amount of data, the FE will also be tested as a covariate in the model. Such analysis will be specified in a separate Pharmacometry analysis plan. Results will be presented separately from the main CSR.

Blood will be collected for M3814 (and 0-demethylated product M467) and avelumab determination according to the following schedules:

Table 11: Pharmacokinetic Sampling Times for Part A and Part FE

Week (Day)	Time (h)	M3814 (Part A)	M3814 (Part FE)	Avelumab (both parts)
Week 1 (Day 1) and	Predose	X	X	X
Week 3 (Day 15)	1	X	X	
	Eol			X (Day 1 only)
	2	X	X	
	3	X	X (Day 15 only)	
	4	X	X	
	6	X	X	
Week 4 (Day 22)	Predose	X	Х	
	2	X	X	
	4		Х	
	6	X	Х	
Week 5 (Day 29)	Predose	X		X
	Eol			X (Part A only)
Week 9 (Day 57)	Predose			X (Part A only)
Week 13 (Day 85)	Predose			Х
Weeks 25, 37, 49	Predose			х
EoT*		X	X	X (Part A only)
30-Day Safety FU (if prior to Week 49)				Х

For both Part A and Part FE, M314 will be administered twice daily, without interruption, in combination with avelumab (1 hour infusion), administered once every two weeks, starting on Day 1 until PD or unacceptable toxicity. In Part FE, subjects will be fed a high fat meal on Day 1 and Day 22 and will be fasted on Day 15. EoI = end of infusion; EoT = end of treatment; FU = follow-up

\* For M3814, only applies if M3814 treatment is stopped. For avelumab if prior to Week 49.

Table 12: Pharmacokinetic Sampling Times for Part B

Week (Day)	Time (h)	M3814	Avelumab
Week 1 (Day 1; FD1)	Predose	х	X
	1	Х	
	Eol		X
	2	X	
	4	X	
	6	X	
Week 1 (Day 2; FD2)	Predose	X	
	2	X	
Week 2 (Day 8; FD6)	Predose	X	
	2	X	
Week 2 (Day 12; FD10)	Predose	X	
	2	X	
	4	X	
	6	X	
Week 3 (Day 15)	Predose		X
Week 5 (Day 29)	Predose		X
	Eol		X
Week 9 (Day 57)	Predose		X
Week 13 (Day 85)	Predose		Х
Weeks 25, 37, 49	Predose		X
EoT*		X	X
30-day Safety FU			X

M3814 will be administered once a day. RT will be given at the dose of 3 Gy per day. M3814 and RT will both be given starting Day 1 for 5 days/week for 2 weeks, at which point both M3814 and RT are discontinued. Avelumab (1 hour infusion) will be administered once every two weeks, starting on Day 1 until PD or unacceptable toxicity. EoI = end of infusion; EoT = end of treatment; FD = fraction day; FU = follow-up.

\* For avelumab, if prior to Week 49.

Table 13: Acceptable Pharmacokinetic Window for Avelumab

Sampling Time	Time From Scheduled Sampling Allowed
Before Bol	Within 120 minutes prior to dose
Eol	Within 15 minutes before Eol

Bol = beginning of infusion; Eol = end of infusion

Table 14: Acceptable Pharmacokinetic Window for M3814

Sampling Time	Time From Scheduled Sampling Allowed	
Predose	Within 60 minutes prior to dose administration	
0.5 to 2 hours postdose	± 20 minutes	
> 2 hours postdose	± 30 minutes	

Samples that are collected outside the specified time windows will be included in the PK parameter estimation (NCA) but will be excluded from the concentration summary and mean concentration plots.

PK concentrations which are erroneous due to a protocol violation (as defined in the CSP), sampling processing or analytical error (as documented in the bioanalytical report) may be excluded from the PK analysis if agreed by the Sponsor. In this case the rationale for exclusion must be provided in the Clinical Study Report (CSR). Any other PK concentrations that appear implausible to the Clinical Pharmacologist/Clinical PK/PD Scientist will not be excluded from the analysis. Any implausible data will be documented in the Clinical Study Report (CSR).

Any PK concentrations or PK parameters excluded from summary statistics will be included in subject listings and flagged; a reason for exclusion will be detailed in the CSR (e.g. a footnote or a table of exclusions). Any flags should be included in the study specific SDTM and ADaM data sets.

The following PK parameters will be reported for M3814 and 0-demethylated product M467 (if available) on Day 1 (D1), Day 15 (D15), and Day 22 (D22) and in Part A and Part FE where data permit. Appropriate adjustments will be made for differences in molecular weight (MW) (M3814 MW = 481.92 gmol; 0-demethylated product M467 MW = 467.12 gmol). Concentration results collected on Day 22, Day 29 (Part A), and EoT will be summarized descriptively.

Cmax Maximum observed concentration.

Cmax/Dose The dose-normalized maximum observed concentration (Part A only). Normalized

using the actual dose, and the formula Cmax/Dose.

Ctrough The concentration observed immediately before next dosing on D15, D22, and D29,

(D29 is Part A only).

Ctrough/Dose The dose-normalized trough concentration. Normalized using the actual dose, and

the formula Ctrough /Dose on D15, D22, and D29, (D29 is Part A only).

AUC0-6 Area under the concentration-time curve (AUC) from time zero to time 6 hours

postdose. AUC0-6 will be based on the estimated concentration at 6 hours and not

the concentration at the actual observation time.

AUC0-6/Dose The dose-normalized AUC from time zero to 6 hours postdose (Part A only).

Normalized using the actual dose, using the formula AUC0-6/Dose.

AUC0-12 AUC from time zero to time 12 hours postdose. AUC0-12,D1 will be based on the

estimated concentration at 12 hours after dosing. AUC0-12,D15 from zero to 12 hours postdose with predose D15 concentration used for estimated concentration at

12 hours (Part A only).

AUC0-12/Dose The dose-normalized AUC0-12 (Part A only). Normalized using the actual dose,

using the formula AUC0-12/Dose.

tmax Time to reach the maximum observed concentration Cmax.

Racc(Cmax) Accumulation ratio for Cmax, calculated as Cmax,D15/Cmax,D1 (Part A only).

Frel(Cmax) Relative bioavailability of Cmax of fed (D22) compared to fasted (D15)

Cmax,fed/Cmax,fasted and Cmax of fed (D1) compared to fasted (D15) Cmax,fed/Cmax,fasted

(Part FE only).

Racc(AUC0-12) Accumulation ratio for AUC0-12 calculated as AUC0-12,D15/AUC0-12,D1 (Part A only).

Frel(AUC0-6) Relative bioavailability for AUC0-6 of fed (D22) compared to fasted (D15)

AUC0-6,fed/ AUC0-6,fasted and as sensitivity analysis AUC0-6 of fed (D1) compared to

fasted (D15) AUC0-6,fed/ AUC0-6,fasted (Part FE only).

λz Terminal first order elimination rate constant.

t½ Apparent terminal half-life,  $t_{\frac{1}{2}} = \ln 2/\lambda_z$ .

The following PK parameters will be reported for M3814 on Day 1 (FD1) and Day 12 (FD10) in Part B where data permit. Concentration results collected on Day 2 (FD2), Day 8 (FD6), and EoT will be summarized descriptively.

Cmax Maximum observed concentration

Cmax/Dose The dose-normalized maximum observed concentration. Normalized using the

actual dose, and the formula Cmax/Dose.

Ctrough The concentration observed immediately before next dosing on FD10 only.

Ctrough/Dose The dose-normalized trough concentration. Normalized using the actual dose, and

the formula Ctrough/Dose on FD10 only.

AUC0-6 Area under the concentration-time curve (AUC) from time zero to time 6 hours

postdose. AUC0-6 will be based on the estimated concentration at 6 hours and not

the concentration at the actual observation time.

AUC0-6/Dose The dose-normalized AUC from time zero to 6 hours postdose. Normalized using

the actual dose, using the formula AUC0-6/Dose.

AUC0-24 Area under the concentration-time curve (AUC) from time zero to time 24 hours

postdose. AUC0-24,FD1 will be based on the estimated concentration at 24 hours after dosing and not the concentration at the actual observation time. AUC0-24,FD10 from zero to 24 hours postdose with predose FD10 concentration used for estimated

concentration at 24 hours.

[figure not shown]
AUC0-24/Dose The dose-normalized AUC from time zero to 24 hours postdose for FD1 and FD10.

Normalized using the actual dose, using the formula AUC0-24,FD1/Dose and

AUC0-24,FD10/Dose.

tmax Time to reach the maximum observed concentration Cmax

Racc(Cmax) Accumulation ratio for Cmax, calculated as Cmax, FD10/Cmax, FD1

The following PK parameters will be reported for avelumab where data permit.

CEOI Concentration observed at the end of infusion period.

Ctrough Concentration observed immediately before next dosing (corresponding to pre-dose or trough concentration for multiple dosing).

Racc(Ceoi) Accumulation ratio for CEOI, calculated as CEOI,D29/CEOI,D1 (Part A and Part B).

Racc(Ctrough) Accumulation ratio for Ctrough, calculated as Ctrough,D57/Ctrough,D15 (Part A and Part B)

The following PK parameters will be calculated for M3814 or M467 for diagnostic purposes and listed, but will not be summarized:

- λz Terminal first order elimination rate constant
- First (λz low) and last (λz up) time point of the time of the log-linear regression to determine λz.
- Number of data points included in the log-linear regression analysis to determine λz.
- Goodness of fit statistic (Rsq,adj) for calculation of λz.

The calculation of the AUC will be performed using the mixed linear-log trapezoidal method. The actual time of blood sampling (14 significant digits or the SAS format Best12) will be used for PK parameter calculation. In cases where the actual sampling time is missing, calculations will be performed using the scheduled time.

Values below the lower limit of quantification of the assay (LLOQ) will be taken as zero for summary statistics of PK concentration data, PK parameter estimation, and for graphical presentations. In case BLQ concentrations occur at the end of the dosing interval (24 h), these will be excluded from the calculation of the AUC0-24.

The regression analysis should contain data from at least 3 different time points in the terminal phase consistent with the assessment of a straight line on the log-transformed scale. Phoenix

[figure not shown]
WinNonlin "best fit" methodology will be used as standard. However, in some cases, further adjustment may be made by the pharmacokineticist, if warranted, after agreement with the Sponsor. The last quantifiable concentration should always be included in the regression analysis, while the concentration at  $t_{max}$  and any concentrations <LLOQ which occur after the last quantifiable data point should not be used.

The coefficient of correlation (Rsq,adj) should be  $\geq$ 0.8000 and the observation period over which the regression line is estimated should be at least twofold the resulting  $t_{1/2}$  itself. If these criteria are not met, then the rate constant and  $t_{1/2}$  will be included in the parameter outputs and descriptive statistics but will be flagged and discussed appropriately. Any flags will be included in the study specific SDTM and ADaM data sets.

The following listings and summary statistics of M3814, 0-demethylated product M467, and avelumab PK concentration and M3814 and 0-demethylated product M467 parameter data will be provided:

- Listing of individual PK concentration data by analyte, part, dose, and scheduled time point
- Listing of individual single dose PK parameters by analyte, part, dose, and day
- Listing of individual multiple dose PK parameters by analyte, part, dose, and day
- Descriptive summary table of PK concentration data by analyte, part, dose, day, and scheduled time point
- Individual concentration-time profiles (linear and semi-logarithmic scales) will be plotted by analyte, dose level and day as spaghetti plots, using actual time points (where available).
   Separate profiles for fed and fasted treatments, Part FE.
- Additional spaghetti plots will be produced (on both linear and semi-log scale) to show the
  concentration-time data per dose level over the entire-time course. Separate profiles for fed and
  fasted treatments, Part FE.
- Arithmetic mean concentrations will be plotted on both linear (±StDev) and semi-logarithmic scales using scheduled time points with all dose levels overlaid per day, and with all days overlaid per dose level. Additional mean plots will be produced (on both linear (±StDev) and semi-log scale) to show the mean concentration-time data per dose level over the entire-time course. Additional individual profiles and mean plots for fed and fasted treatments: overlay plots D1/D15 and D15/D22 for Part FE.
- Scatter plots of dose-normalized Cmax, dose-normalized AUC0-6, and dose-normalized AUC0-12 or dose-normalized AUC0-24 (as applicable) against dose (all days).
- Paired data plots of Cmax and AUC0-6 against fed and fasted, Day 22 and Day 15, Day 1 and Day 15 respectively, for Part FE.

All descriptive summaries of PK data will be performed using the PK Analysis Set. Individual PK data will be listed using the Safety Analysis Set. The mean concentration-time profiles and PK parameter plots will be plotted using the PK Analysis Set and the individual subject concentration-time profiles will use the Safety Analysis Set.

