 - Part B will be initiated once a first dose level of Part A has been declared as safe and tolerable by the Safety Monitoring Committee (SMC).
- Part FE aims to evaluate the FE on PK of M3814 following administration of M3814 in combination with avelumab under fasted and fed conditions. Only doses of M3814 already declared as safe and tolerable in Part A by the SMC will be investigated in this part of the study.
- The tablet formulation of M3814 will be used in this study.
- Additional dosing regimens of M3814 and avelumab (Part A and Part FE) or M3814, avelumab, and RT (Part B) may be introduced by protocol amendment to be explored.
- An increase in the sample size for Part A, Part B, and/or Part FE of the study to accommodate
 additional dose levels may be added by protocol amendment.
- In addition, expansion cohorts in defined advanced solid tumor indications may be added by amendment to explore preliminary efficacy of the combination regimens studied in Part A and/or Part B.

Number of Participants:

In this study, for each part (A and B) the sample size will depend on the number of dose-limiting toxicities (DLTs) observed at the different dose levels and the number of tested or expanded dose levels for M3814 as dose escalation will be guided by a Bayesian logistic regression model with overdose control.

A two-parameter logistic model will be used to describe the dose-toxicity relation for M3814. CCI clinical data of M3814 are used to set up the model. It is anticipated that 6 to 30 participants in Part A (3 to 6 participants at each dose level) and 6 to 24 participants in Part B (3 to 6 participants at each dose level) may be needed. In addition, 6 to 12 participants will be enrolled in Part FE to assess the FE on PK of M3814. Thus, the total number of participants may be 18 to 66.

Study Intervention Groups and Duration:

Part A: M3814 will be administered twice daily (BID) continuously, in combination with avelumab 800 mg once every 2 weeks (Q2W) starting on Day 1 until progressive disease (PD) or unacceptable toxicity. The starting dose of M3814 in Part A will be 100 mg BID. Subsequent doses and schedules will be determined by the SMC.

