3.3 Part FE

Table 10 Study Objectives and Endpoints – Part FE

Objectives	Endpoints (Outcome Measures)							
Primary								
To determine and compare the pharmacokinetic profile of M3814 under fasted and fed conditions	Area under the M3814 plasma concentration-time curve (AUC) from time zero to the last quantifiable sampling time (AUCot), and maximum M3814 plasma concentration observed (Cmax)							
Secondary								
Safety								
To evaluate the safety profile and tolerability of M3814 in combination with avelumab under fasted and fed conditions	 Occurrence of treatment-emergent adverse events and treatment-related adverse events according to the NCI-CTCAE v 5.0, and serious adverse events 							
	 Occurrence of abnormalities (Grade ≥ 3) in laboratory test values, markedly abnormal vital sign measurements, markedly abnormal physical examination measurements, clinically significant abnormal ECG, marked changes in ECOG PS 							
Immunogenicity								
To evaluate the immunogenicity of avelumab in combination with M3814 under fasted and fed conditions	Immunogenicity as measured by ADA							
Efficacy								
To evaluate the preliminary antitumor activity of M3814 when given in combination with avelumab in participants with locally advanced or advanced solid tumors, under fasted and fed conditions	 Confirmed BOR, DOR assessed from CR or PR until PD, death, or last tumor assessment, and PFS time according to RECIST v 1.1 as assessed by the Investigator 							
	 Tumor size measurement based on Investigator assessment according to RECIST v 1.1 from the first study interventions dose until confirmed PD or start of new cancer treatment 							
	Overall Survival							
Exploratory								
CCI								

ADA=antidrug antibody, ADME=absorption, distribution, metabolism, and excretion, BOR=best overall response, CR=complete response, DOR=duration of response, ECG=electrocardiogram, ECOG PS=Eastern Cooperative Oncology Group Performance Status, Fc_YR=Fc receptors for IgG, NCI-CTCAE=National Cancer Institute-Common Terminology Criteria for Adverse Events, PD=progressive disease, PFS=progression-free survival, CCI PR=partial response, RECIST=Response Evaluation Criteria In Solid Tumors.

4 Study Design

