6.6.2 Dose Selection (Part FE)

The starting dose of M3814 would be 200 mg total daily dose given as 100 mg BID. Subsequent doses and schedules will be determined based on the PK and safety data generated in previous

cohorts of Part A and Part FE and should be within the dose ranges already declared safe and tolerable in Part A. Avelumab will be administered Q2W as an IV infusion over 1 hour, starting on Day 1, at a fixed dose of 800 mg in all dose levels. Guidance on premedication is given in Section 6.5.5.

The FE Assessment Period is considered completed and a participant evaluable for subsequent dose level decisions, when the PK and minimum safety evaluations have been performed (hematology, chemistry, and clinical assessments), and the participant has received:

 at least 80% of the planned doses of M3814 (i.e., 34 of 42 doses with BID dosing regimen) and 100% of the planned avelumab doses (2 administrations) during the FE Assessment Period of 3 weeks.

The results from Part FE will be reviewed and evaluated by the Sponsor and if deemed necessary by the SMC to determine a potential impact on the study dosing recommendations for M3814 and/or safety profile of M3814 when given in combination with avelumab.

Cohorts of at least 3 participants each will be treated at the same dose level of M3814 (starting dose: 100 mg tablet formulation, BID) in combination with avelumab. On the day of avelumab administration, M3814 can be given prior to the start or just after the end of avelumab infusion. A preselected set of acceptable doses as described in Table 12, will be considered once declared as safe and tolerable in Part A, however, doses which are not part of the prespecified set may be chosen as well, as long as they are within the prespecified dose ranges based on considerations of PK and safety data generated in previous cohorts. If the sample size in Part FE has to be increased to accommodate additional dose levels, a protocol amendment with rationale will be submitted prior to implementation. The Sponsor and/or the SMC may decide to continue or stop the assessment of FE in subsequent dose level (s). This decision will be based on PK and safety data generated in the previous cohorts in Part A and/or Part FE and/or emerging data from the clinical studies which are currently evaluating the human pharmacology, safety, and tolerability of M3814. It is anticipated that 6 to 12 participants (3 to 6 participants at each dose level) may be needed.

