9.1 Statistical Hypotheses

No formal statistical hypothesis will be tested, as the study is designed to be exploratory.

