#### Significance level

All statistical tests mentioned in this IAP are to be regarded as exploratory. If confidence intervals (CIs) are to be calculated, these will be two-sided with a confidence probability of 95%, unless otherwise specified in this IAP.

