# 9.2.2 Presentation of Pharmacokinetic Parameter Data

Pharmacokinetic parameter data will be descriptively summarized using: n, Mean, StDev, CV%, Min, Median, Max, geometric mean (GeoMean), and the geometric coefficient of variation (GeoCV). For time to reach maximum observed concentration ( $t_{max}$ ), only n, Min, Median, and Max will be reported. In cases with  $n \le 2$ , only n, Min, and Max will be reported. The PK parameter maximum observed plasma concentration ( $t_{max}$ ) will be reported with the same precision as the source data. All other PK parameters will be reported to 3 significant figures. In export datasets, as well as in the SDTM PP domain, PK parameters will be provided with full precision, and will

CONFIDENTIAL

not be rounded. Descriptive statistics of PK parameter data will be calculated using full precision values and rounded for reporting purposes only.

The following conventions will be applied when reporting descriptive statistics of PK parameter data:

Mean, Min, Median, Max, GeoMean: 3 Significant digits StDev: 4 Significant digits CV%, GeoCV%: 1 decimal place

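### Part FE's primary fed/fasted contrast has no planned confidence interval, so the report would not show directly that a ratio near 1 from 3 to 6 participants is usually inconclusive

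*SAP*

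**What the plan says.** Protocol 3.3 (Table 10) gives the Part FE primary objective: "To determine and compare the pharmacokinetic profile of M3814 under fasted and fed conditions". Protocol 6.6.2 sets the size: "It is anticipated that 6 to 12 participants (3 to 6 participants at each dose level) may be needed".

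SAP section 5 sends the endpoint to SAP 16.1. There the food effect on Cmax is the relative bioavailability "of fed (D22) compared to fasted (D15"), with Day 1/Day 15 alongside. For AUC0-6 it is the same Day 22/Day 15 ratio and "as sensitivity analysis AUC0-6 of fed (D1) compared to" the fasted Day 15 value. Section 16.1 also lists overlay and paired plots.

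The statistics come from SAP 9.2.2: "Pharmacokinetic parameter data will be descriptively summarized using: n, Mean, StDev, CV%, Min, Median, Max, geometric mean (GeoMean") and the geometric CV. With two or fewer values, only n, minimum and maximum are given. SAP 9.1 sets a level for intervals without calling for one here: "If confidence intervals (CIs) are to be calculated, these will be two-sided with a confidence probability of 95" per cent.

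Protocol 9.1 frames the whole study: "No formal statistical hypothesis will be tested, as the study is designed to be exploratory".

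**The concern.** The contrast is the primary endpoint of its study part, and it is the only primary endpoint built on a comparison. The secondary efficacy endpoints in SAP 14.1, 14.2, 14.4 and 14.5 all have 95% intervals specified. This one has none, and no model from which an interval would follow.

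The result is used. The note to Protocol Table 12 bases movement between Part FE dose levels on the food-effect data of the preceding cohort, with safety data also considered. That cohort may hold 3 participants. Protocol 6.6.2 has the results reviewed for a possible effect on dosing recommendations. A point ratio near 1 shown without its uncertainty invites more confidence than so few participants can support.

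**Working it through.** **1. The plan's own figures.** Two dose levels of 3 to 6 give 2 x 3 = 6 to 2 x 6 = 12 for Part FE. Across parts, 6 + 6 + 6 = 18 and 30 + 24 + 12 = 66, which matches the synopsis: "Thus, the total number of participants may be 18 to 66". The available text states no power, precision target or margin for Part FE, so there is no such figure to reproduce. Protocol 9.2 (sample size) is not in the available text and cannot be judged.

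**2. Could an interval come from elsewhere?**
- SAP 9.1 fixes the level only where an interval is to be calculated.
- Protocol 9.4.3 allows 95% intervals for means of continuous variables where appropriate. That is optional and is not a ratio of geometric means. SAP 9.2.2, the specific rule for PK parameters, does not take it up.
- SAP 16.1 would test food effect as a covariate in a population PK model if the data suffice. That work sits in a separate plan and is reported outside the main study report.

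None of these requires an interval for the ratio.

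**3. How wide would it be?** The log of a within-participant ratio is a difference of two logs, each with variance ln(1 + CV²), where CV is the within-participant CV. Hence

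SD = sqrt(2 x ln(1 + CV²)), and the 90% CI = ratio x exp(± t(0.95, n-1) x SD / sqrt(n)).

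Example with CV 30% and n = 6: SD = sqrt(2 x ln 1.09) = 0.415. The half-width is 2.015 x 0.415 / sqrt(6) = 0.342. Around an observed ratio of 1.00 this gives exp(±0.342) = 0.71 to 1.41.

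The documents give no CV, so the values below are assumptions. 90% interval around an observed ratio of 1.00:

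| n | CV 20% | CV 30% | CV 50% |
|---|---|---|---|
| 3 | 0.62-1.60 | 0.50-2.01 | 0.32-3.08 |
| 6 | 0.79-1.26 | 0.71-1.41 | 0.58-1.73 |
| 12 (pooled) | 0.86-1.16 | 0.81-1.24 | 0.71-1.41 |

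At the SAP's default 95% level and CV 30%, the intervals are 0.36-2.80, 0.65-1.55 and 0.77-1.30. At a favourable CV of 15%, the 90% intervals are 0.70-1.43, 0.84-1.19 and 0.90-1.12.

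**4. How often would a real effect look like none?** Take a true ratio of 1.30 and CV 30%. With n = 6 the standard error is 0.415 / sqrt(6) = 0.169. The chance that the observed geometric mean ratio falls between 0.90 and 1.10 is Φ((ln 1.1 - ln 1.3)/0.169) - Φ((ln 0.9 - ln 1.3)/0.169), or about 15%. It is 18% for n = 3 and 8% for n = 12.

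**5. How often would no effect be shown as such?** Take an illustrative margin of 0.80-1.25 (an assumption; the plan has none) and a true ratio of 1. By simulation, the chance that the 90% interval lies inside the margin is:
- CV 20%: 7%, 19% and 66% for n = 3, 6 and 12
- CV 30%: 2%, 4% and 16%
- CV 40%: 1%, 1% and 3%

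**The case against.** The strongest reply is that the precision is not lost. The ratios are listed as PK parameters, so for n above 2 SAP 9.2.2 gives their n, geometric mean and geometric CV. A reader can then form GeoMean x exp(± t x sqrt(ln(1 + GeoCV²)) / sqrt(n)). With CV 30% the ratio's GeoCV is sqrt(1.09² - 1) = 43%, which returns the same SD of 0.415. This stands, so it would be wrong to say that no precision information exists. What is missing is the interval itself. The recovery also leans on 9.2.2 alone, because the output list in 16.1 names parameter listings and a concentration summary table but no parameter summary table.

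A second reply is that the study is exploratory. That rules out a demand for a test, but an interval is estimation. The same exploratory SAP provides intervals for its secondary endpoints.

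Third, a reader might infer that the sponsor means to declare no food effect, or that these data can never support such a reading. The documents support neither. No passage plans that conclusion or sets an equivalence margin. With 12 pooled participants and a CV of 20%, the 90% interval of 0.86-1.16 is fairly tight.

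A reader might also infer that dosing recommendations rest on this ratio alone. Protocol 6.6.2 speaks of a potential impact, and decisions to continue or stop also draw on safety, Part A and other studies.

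Finally, an interval cannot repair the design. The order is fixed: Day 1 fed, Day 15 fasted, Day 22 fed (Protocol 6.6.5.3). Day 22 also lacks the 1 h and 3 h samples taken on Day 15 (SAP Table 11). This stands and limits what the fix can claim.

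**Conclusion.** The point holds as a gap in planned reporting. The primary Part FE contrast has point summaries and plots but no interval, and nothing elsewhere in the available text requires one.

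Its size depends on the within-participant CV, which is assumed, and on n. For one dose level of 3 to 6 participants, an observed ratio of 1.00 leaves room for changes of about a fifth to a quarter either way in the best tabulated case (CV 20%, n = 6). With 3 participants at CV 30%, it leaves room for a halving or a doubling. Pooling to 12 makes the estimate reasonably precise at CV 20% and much less so at 50%.

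The calculations assume roughly normal log ratios and, for n = 12, a common food effect across dose levels. They describe random error only. Bias from the fixed order or from unequal sampling is outside them. So is the carry-over of first-dose versus repeated-dose exposure into the Day 1/Day 15 ratio.

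**What to change.** In SAP 16.1:
- Analyse log Cmax and log AUC0-6 as paired data, with participant as block, condition as a fixed effect, and dose level as a factor when pooled.
- Report the fed/fasted geometric mean ratio with a two-sided interval for Day 22/Day 15, by dose level and pooled. Give Day 1/Day 15 as sensitivity for both parameters.
- State the confidence level. If 90% is chosen, record it as an exception to the 95% default in SAP 9.1.
- State that a ratio near 1 with a wide interval is inconclusive.
- State that the interval does not account for the fixed fed-fasted-fed order, or for Day 22 lacking the 1 h and 3 h samples taken on Day 15.

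The cost is a few lines of code and one table. No new data, visits or participants are needed. The downside is that the interval may look wide, particularly in a cohort of 3.
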